2.5.3.1 Worsening of cardiac function

For the analysis of worsening of cardiac function, patients who have not experienced a worsening of cardiac function will be censored at the last date when echocardiography results are available.

2.5.3.2 Hospitalization for congestive heart failure

For the analysis of hospitalization for congestive heart failure, patients who have not experienced any hospitalization for congestive heart failure will be censored at the last contact date.

2.5.3.3 Liver function impairment

For the analysis of liver function impairment, patients who have not experienced any liver function impairment will be censored at the last date when laboratory values for ALT, AST and bilirubin are available.

2.5.3.4 Liver cirrhosis

For the analysis of liver cirrhosis, patients who have not experienced liver cirrhosis will be censored at the last contact date.

2.5.3.5 Progression to AML

AML progression will be determined by the bone marrow aspirate. In case of AML suspicion, bone marrow aspirate will be performed to confirm AML at any time until study evaluation completion. Thus, for the analysis of progression to AML, patients who have not experienced progression to AML will be censored at the last contact date.

2.5.3.6 Increase in serum ferritin

For the analysis of time from randomization to the first occurrence of serum ferritin > 2 times the baseline value at two consecutive assessments (at least two weeks apart), patients who did not experience such an increase in serum ferritin will be censored at the last date when serum ferritin was available or at the date of randomization if no post baseline serum ferritin is available.

2.5.4 Sensitivity and supportive analyses

The two main sensitivity analyses for the primary efficacy analysis (event-free survival) will be based on the two alternative censoring rules. Otherwise, the same statistical methods will be used for the primary analysis of event-free survival. A third sensitivity analysis using the

same methodology will address the issue of partial data for the composite endpoint (i.e., a patient with some missing data but not all of the components of composite endpoints).

For the first main sensitivity analysis patients with premature discontinuation of randomized study treatment and subsequent treatment with marketed iron chelation therapy (including Exjade[®]) will be censored at the date of first administration of the subsequent iron chelation therapy.

For the second main sensitivity analysis patients with premature discontinuation of randomized study treatment (regardless of whether they were subsequently treated with marketed iron chelation therapy) will be censored at the date of last administration of randomized study treatment.

The third sensitivity analysis will employ the following censoring rules:

- If an event is documented after three or more consecutive missing biochemistry laboratory assessments (regarding results for ALT, AST, and total bilirubin), the event-free survival time of these patients will be censored at the date of the last assessment with complete information for ALT, AST, and total bilirubin.
- If an event is documented after two or more consecutive missing echocardiogram (ECHO) assessments (for left ventricular ejection fraction), the event-free survival time of these patients will be censored at the date of the last ECHO assessment.
- If an event is documented after at least three consecutive missing biochemistry laboratory assessments (ALT, AST, and total bilirubin) and at least two consecutive missing ECHO assessments simultaneously, the event-free survival will be censored at the date of the last assessment with both biochemistry laboratory and ECHO assessments completed.
- As the three other components, 'hospitalization for congestive heart failure', 'liver cirrhosis' and 'Progression to AML', i.e. assessed in unscheduled examinations, missing assessments for them cannot be determined.

Sensitivity analyses include:

- Point estimate and two-sided 95% confidence interval for the adjusted HR from a Cox proportional hazard regression model stratified for the randomization factors with adjustment for demographic or baseline characteristics of clinical interest. The adjustment will be made for age (≥65 vs < 65), Asian vs non-Asian, MDS risk group (low vs intermediate).
- Statistical analyses based on the PPS instead of the FAS.

Supportive analyses include:

- KM curves by treatment and unadjusted HR (point estimate and two-sided 95% confidence interval) for each of the strata defined by the randomization factors.
- KM curves by treatment and unadjusted HR (point estimate and two-sided 95% confidence interval) for each component of event-free survival (overall survival is also a secondary efficacy endpoint, see Section 2.7.1.1).
- Number of deaths and non-fatal events adjudicated by the endpoint adjudication committee

- Primary endpoint analyses will be repeated for the FAS excluding patients from one site due to data integrity issue. The time to event analyses will be performed and will include.
 - Stratified log-rank test and Cox-regression model for event-free survival
 - Overall summary of event free survival

These patients will be excluded from per-protocol set for the sensitivity analyses.

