For each treatment group, survival functions for time from randomization to the composite primary endpoint (event-free survival) will be estimated and displayed by the Kaplan-Meier method.

Sensitivity/supportive/exploratory analyses for the primary endpoint:

- Point estimate and two-sided confidence interval for an adjusted hazard ratio from a Cox proportional hazard regression model stratified for the randomization factors; adjustment for (partly data driven) demographic and/or baseline characteristics of clinical interest:
- Unadjusted hazard ratio estimates for each of the strata defined by the randomization factors;
- Analysis analog to the primary statistical analysis but patients with premature discontinuation of randomized study treatment will be censored at the day of last administration of randomized study treatment;
- Summary of the types of events observed;
- Statistical analyses based on the PPS instead of the FAS.

Statistical analysis methods for secondary efficacy endpoints:

Analyses will be described in the full clinical study protocol.

Statistical analysis methods for safety endpoints:

Following (Fleming 2008), the goal of this exploratory trial is not to determine whether there is significant evidence to rule out the null hypothesis of no increased risk.

In contrast, the objective here is to exclude levels of increased risk (for pre-specified adverse events mentioned in the Endpoints section) that would be clinically unacceptable in the context of the level of benefit that is likely to be provided by iron chelation using deferasirox in MDS patients with iron overload. Therefore, two-sided 95% confidence intervals for risk (or hazard, if applicable) ratios will be calculated. Incidences of treatment emergent (serious) adverse events (including combinations of MedDRA terms as defined by Standardized MedDRA Queries) will be summarized by treatment group. Laboratory data will be summarized using descriptive statistics and shift tables (using CTCAE classification where available) by treatment group.

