## Patients meeting a non-fatal component of the composite primary endpoint

The end of study treatment will occur if a patient meets any non-fatal component of the composite primary endpoint (Section 3.1.1) confirmed by the Endpoint Adjudication Committee (EAC). His/her individual randomized study treatment will be unblinded and discontinued at that time. The subsequent iron chelation treatment is subject to the patient's

and the investigator's decision. After termination of study treatment, all patients will continue to be followed for safety and non-fatal components of the primary endpoint during the evaluation period at visits occurring every three months. Subsequent to the evaluation period, or at the end of treatment if a patient and treating physician decide that a patient will not participate in the evaluation period, patients will be followed every 6 months for iron chelation therapies and overall survival ("Survival Follow-up").

All suspected endpoint events will be reviewed and adjudicated by the EAC; however, only the first confirmed endpoint for a patient will be counted for the composite primary endpoint. The role of the EAC is to ensure that all events that have been reported are judged uniformly using the same criteria. The EAC is blinded to study treatment.

[figure not shown]

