#### 6.7.6.1 End of Treatment

If study drug is discontinued, IVRS is to be notified and the End of Treatment Page is to be completed with the 'last known date the patient took study drug' and one of the following reasons:

- Adverse Event
- Abnormal laboratory value(s)
- Abnormal test procedure result(s)
- Protocol deviation
- Subject withdrew consent
- Lost to follow-up
- Administrative problems
- Death
- Disease progression
- Pregnancy
- Physician's decision
- Treatment duration completed as per protocol
- Subject / Guardian Decision

• Study terminated by sponsor

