For the second main sensitivity analysis described in Section 10.4.4, patients with premature discontinuation of randomized study treatment (regardless of whether they were subsequently

treated with marketed iron chelation therapy) will be censored at the date of last administration of randomized study treatment.

The third sensitivity analysis described in Section 10.4.4 will employ the following censoring rules.

- If an event is documented after three or more consecutive missing biochemistry laboratory assessments (regarding results for ALT, AST, and total bilirubin), the event-free survival time of these patients will be censored at the date of the last assessment with complete information for ALT, AST, and total bilirubin.
- If an event is documented after two or more consecutive missing echocardiogram (ECHO) assessments (for left ventricular ejection fraction), the event-free survival time of these patients will be censored at the date of the last ECHO assessment.
- If an event is documented after at least three consecutive missing biochemistry laboratory assessments (ALT, AST, and total bilirubin) and at least two consecutive missing ECHO assessments simultaneously, the event-free survival time will be censored at the date of the last assessment with both biochemistry laboratory and ECHO assessments completed.
- As the three other components, 'hospitalization for congestive heart failure', 'liver cirrhosis', and 'Progression to AML' are symptom-based, i.e., assessed in unscheduled examinations, missing assessments for them cannot be determined.

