2.1.2.3 Date of last administration of study treatment

The date of last administration of study treatment is defined as the last date when a non-zero dose of study treatment was administered as per Dose Administration eCRF.

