2.1.2.9 On-treatment assessment/event and observation periods

The overall observation period will be divided into three mutually exclusive segments:

- 1. *pre-treatment period*: before the first administration of study treatment
- 2. *on-treatment period*: from date of first administration of study treatment to 28 days after date of last actual administration of any study treatment (including start and stop date)
- 3. *post-treatment period*: starts on day 28+1 after last administration of study treatment.

Per study design, there will be two additional observation periods:

- 4. *study evaluation period:* starts on day 29 after last administration of study treatment until study evaluation completion period (visit frequency every three months)
- 5. **survival follow-up period:** starts after study evaluation completion visit until LPFV plus three years or death. If a patient declines to participate in the evaluation period, the survival follow-up period will start on day 29 after last administration of study treatment until LPFV plus three years or death (visit frequency is every 6 months).

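### The second main sensitivity analysis of event-free survival censors at the last dose with no window, so deaths after a premature stop, and possibly deaths on drug, drop out

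*SAP*

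**What the plan says.** SAP 2.5.4 names two main sensitivity analyses of event-free survival. In the second, premature discontinuers, whether or not they later received a marketed chelator, "will be censored at the date of last administration of randomized study treatment". Protocol 10.4.3 gives the same rule, and the protocol synopsis agrees: "patients with premature discontinuation of randomized study treatment will be censored at the day of last administration of randomized study treatment".

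SAP 2.1.2.3 fixes the date as the "last date when a non-zero dose of study treatment was administered as per Dose Administration eCRF". None of these places adds a window after the last dose, defines premature discontinuation, or says how an event close to the stop is ordered against the censoring date.

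Three other provisions matter:

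- Protocol 6.7.6.1 lists the reasons recorded when study drug ends. Death is one of them, separate from completing treatment as planned.
- Protocol Section 4 says "The end of study treatment will occur if a patient meets any non-fatal component of the composite primary endpoint", subject to confirmation by the Endpoint Adjudication Committee (EAC). Protocol Section 10 dates an event that needs later confirmation at its first instance.
- SAP 2.1.2.9 defines an on-treatment period running "from date of first administration of study treatment to 28 days after date of last actual administration of any study treatment". The censoring rule does not use it.

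**The concern.** Death from any cause is a component of the primary endpoint. A patient who stops drug and later dies is always censored before the death. A patient who dies while on drug usually took the last dose on an earlier day. If that death is treated as a premature discontinuation, it too becomes a censored observation.

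Non-fatal events are treated unevenly. An EAC-confirmed event that leads to the stop normally precedes the last dose and stays in. An event that follows the end of dosing is lost. The protocol allows such sequences. Interruption is to be considered for unexplained cytopenia (6.7.1.10), and if dosing never resumes, AML diagnosed by marrow later falls after the last dose. A heart-failure admission after dosing has ceased is lost in the same way.

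Patients may therefore be censored because they are deteriorating, which conflicts with the independent-censoring assumption of the Cox model and log-rank test. The analysis is weighted towards non-fatal events on drug, and a result that matches or differs from the primary one is hard to interpret. The discarded events are available, because protocol 6.7.5.2 continues endpoint follow-up after treatment ends.

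**Working it through.** The plan gives no figure to reproduce, and no rates of death or discontinuation. The check is therefore one of date order, followed by an illustration on assumed inputs.

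**Date order under the rule** (an event counts if dated on or before the last non-zero dose)

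| Situation | Order of dates | Result |
|---|---|---|
| Death after a premature stop | last dose, then death | removed |
| Death on drug, dose taken that day | same day | kept |
| Death on drug, no dose that day | last dose, then death | removed if death counts as premature discontinuation; kept if not |
| Non-fatal event, EAC confirmation, stop | event, then last dose | normally kept |
| Dosing ceases, then non-fatal event | last dose, then event | removed |

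**Illustration for deaths.** Assumed, not from the documents: follow-up uniform over 3 to 8 years; first-event hazards of 0.10 per year for death and 0.05 for non-fatal events; other discontinuation at 0.2 to 0.6 per year; a share p of 10% to 50% of patients dying on drug take a dose on the day of death, the rest having a gap of 1 day plus an exponential time with mean 10 days.

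Let q be the share of first-event deaths that occur before any other discontinuation. With total hazard h = 0.15 + discontinuation rate:

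P(death first, on drug) = (0.10/h) × [1 − (e^(−3h) − e^(−8h))/(5h)]

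Dividing by the same expression with h = 0.15, which is 0.368, gives q ≈ 0.65, 0.46 and 0.35 for discontinuation rates of 0.2, 0.4 and 0.6.

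- Current rule, deaths on drug counted as premature discontinuation: share kept = q × p, from 0.35 × 0.1 = 0.035 to 0.65 × 0.5 = 0.325. Simulation with these inputs gives 3.6% to 32.6% kept, so about 67% to 96% removed.
- Current rule, deaths on drug counted as events: share kept ≈ q, so 1 − 0.65 = 35% to 1 − 0.35 = 65% are still removed.
- Counting events to last dose + 28 days: P(gap ≤ 28 days) = p + (1 − p)(1 − e^(−2.7)), which is 0.94 at p = 0.1 and 0.97 at p = 0.5. So nearly all deaths on drug return. Simulation gives about 35% to 64% of first-event deaths kept.

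**Non-fatal events.** Among those arising before any other discontinuation, the share kept depends on how often dosing ceases before the event: about 90%, 50% or 0% if it does so in 10%, half or all cases. With deaths included, about 2% to 41% of all first events remain under the current rule on the stricter reading of death.

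**Direction.** Take constant hazards and the limiting case where all deaths are removed and all non-fatal events kept. With equal placebo hazards, HR 0.6 for death and 1.0 for non-fatal events, the composite HR is (0.6 + 1.0)/2 = 0.80, and about 1.0 without deaths. If the two HRs are swapped, the composite is again 0.80 but becomes about 0.6 without deaths. With placebo hazards in the 2:1 ratio assumed above, the first case starts from (2 × 0.6 + 1.0)/3 = 0.73. The shift can go either way. These figures show only the change in event mix; they do not measure bias from informative censoring.

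**The case against.** The strongest reply is that the finding depends on an undefined term. The end-of-treatment list also includes planned completion and sponsor termination, so being on it does not make an ending premature. Event-free survival counts death from any cause, so a programmer could reasonably treat a patient dosed until death as having an event. That stands: for deaths on drug the defect is an ambiguity. It does not help deaths after an earlier premature stop, which go on either reading.

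Two stronger readings are tempting. A reader might infer that any event that made the patient stop is removed, because the literal wording has no clause giving precedence to an earlier event. The documents do not support this: event-free survival runs to the first documented event, confirmed events are dated at first instance, and the protocol stops drug only after confirmation, so such events normally precede the last dose. A reader might also infer that almost every death is shown to be removed. The documents give neither the timing of deaths relative to dosing nor discontinuation rates, so the percentages above are illustrations.

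The stakes are also limited, and this stands. The primary analysis censors irrespective of adherence. Overall survival and each component are analysed separately. The first main sensitivity analysis censors only at later chelation, so it keeps deaths in patients who did not switch. The trial is exploratory. Finally, the 28-day period is labelled in the protocol as a safety period. SAP 2.7.1.8 nevertheless uses it for infections, a secondary efficacy endpoint.

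**Conclusion.** The concern holds in a limited form. As written, the rule removes every death after a premature stop and every non-fatal event dated after dosing ceased, and it leaves open whether deaths on drug are removed too. Censoring is therefore likely informative, and the comparison with the primary result is hard to read in either direction. This is more than missing detail, because the loss of deaths after a premature stop follows from the rule as stated.

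The size cannot be computed from the documents. On the assumed inputs, 35% to 65% of first-event deaths are lost on the favourable reading of death on drug and about 67% to 96% on the stricter one. It would go too far to say that the analysis has no value or that the primary estimate is at risk: an on-drug analysis has a recognised if limited purpose, and the primary analysis is untouched. The optional IPCW or RPSFT work in SAP 5.5.4 concerns switching to new chelators and does not address this censoring. The rule should be changed because it governs one of only two main checks on the primary endpoint and the repair is cheap.

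**What to change.** In SAP 2.5.4, for the second main sensitivity analysis:

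1. Count any primary-endpoint event dated on or before last dose + 28 days; otherwise censor premature discontinuers at last dose + 28 days, or at the primary-analysis censoring date if that is earlier.
2. Define premature discontinuation, and state that death as the reason for ending treatment is an event and not a premature discontinuation.
3. Report, per arm, how many deaths and non-fatal events the rule censors.

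The current rule is also in protocol 10.4.3 and the synopsis, so list the change in SAP Section 4 as a departure from the protocol. No new data are needed: protocol 6.7.5 already requires a 28-day follow-up for all patients who stop drug. The cost is a short text change, a revised derivation and one small table.

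The downside is that up to 28 days of off-drug time enters the analysis, possibly with some new chelation, since SAP 2.4.5.2 tabulates chelation reported within 28 days of stopping. Deaths later than that are still censored, so the change reduces the problem without curing it. That is why the per-arm counts are needed.

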2.6 Analysis of the key secondary objective

There is no key secondary objective for this study.

2.7 Analysis of secondary efficacy objective(s)

2.7.1 Secondary efficacy endpoints

All analyses of secondary efficacy endpoints will be based on the FAS.

If applicable, nominal significance levels will be set to one-sided alpha = 0.025; all confidence intervals will be two-sided using an ordinary confidence level of 95%.

2.7.1.1 Hematologic improvement

Hematologic improvement (HI) in terms of erythroid response during treatment will be assessed based on International Working Group (IWG) criteria (Cheson 2006).

The variable used in the analysis of HI will be the proportion of patients who satisfy the erythroid response criteria; namely,

• Hemoglobin increased $\geq 1.5 \text{ g/dL}$

OR

Reduction of ≥ 4 units of RBC transfusions over 8 weeks, in comparison to 8 weeks' pretreatment values, and lasting at least 8 weeks.

For purposes of calculating the reduction in transfusions component of this endpoint, a transfusion unit is defined as 185 mL of PRBC (Cohen Glimm Porter 2008). According to IWG criteria, HI is measured in patients with pre-treatment hemoglobin levels of less than 11 g/dL or RBC transfusion dependence. The definition of transfusion dependency is based on IWG criteria (Cheson 2006). All patients included in this study are transfusion dependent. In order to measure hemoglobin increase, the last hemoglobin value measured prior to randomization will be used as the pretreated value. If 2 pre-treated (prior randomization) hemoglobin values are available and each is at least 7 days after any transfusion, an average of the 2 values will be used to determine the pre-treatment hemoglobin level. All RBC transfusions regardless of pre-transfusion hemoglobin level, will count in the RBC transfusion response criteria. If any pre-treatment hemoglobin value or transfusion history over 8-week period cannot be determined, they will not be a part of risk set and will not be included in the percentage calculation.

All episodes of HI in the patient will be considered.

The percentage of responders will be summarized for the two treatment groups and $100(1-\alpha)\%$ confidence intervals with α of 0.05 will be provided. The 95% confidence limits for the difference of two proportions will be derived by the Wilson score test (see Section 5.5.3).

Overall survival

Overall survival (OS) will be evaluated in patients treated with either deferasirox or placebo. The variable used in the analysis of overall survival is time to death measured in days. It is defined as date of death (irrespective of cause) minus date of randomization plus 1.

Censoring is described in Section 2.7.3.1. The estimation of survival functions and the Cox model to estimate the HR are defined in Section 2.5.2.2 and Section 2.5.2.3. An exploratory statistical test will be performed analogously to the description in Section 2.5.2.4.

The Kaplan-Meier curves, medians, and Kaplan-Meier estimates with 95% confidence intervals at specific time points will also be displayed by treatment and stratum.

In Kaplan-Meier plots, statistics such as p-value, hazard ratio, etc. will also be displayed. Note that only nominal p-values are provided with no statistical interpretation.

Survival information will be listed. The listing will include if patients survived (Yes/No), last contact date, study day, date of death if not survived and principal cause of death.

Unless otherwise specified, all time-to-event analysis will be analyzed in a similar fashion.

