### OR

• Reduction of ≥ 4 RBC transfusions/8 weeks

in comparison to pre-treatment values and lasting at least 8 weeks. According to IWG criteria, HI is measured in patients with pre-treatment hemoglobin levels of less than 11 g/dL or RBC transfusion dependence. Pre-treatment hemoglobin levels must not be influenced by transfusions (no transfusion received for at least one week preceding the hemoglobin measurement). The last hemoglobin value measured prior to randomization will be used as the pre-treatment value. (If 2 pre-treatment Hemoglobin values are available and each is at least 7 days after any transfusion, an average of the 2 values will be used to determine the pre-treatment hemoglobin value). Similarly, measurements after randomization influenced by preceding transfusions within one week will not contribute to the response criteria. All RBC

transfusions regardless of pre-transfusion hemoglobin level will count in the RBC transfusion response evaluation.

All episodes of HI in the patient will be considered.

The percentage of responders will be reported for the two treatment groups. The equality of proportions in the two groups will be analyzed by an exploratory test. Further details will be described in the RAP.

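### Read literally, SAP 2.7.1.1 drops the protocol's 8-week duration from the hemoglobin limb of hematologic improvement and omits its one-week post-transfusion exclusion; SAP Section 4 declares neither change

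*SAP*

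**What the plan says.** Protocol 10.5.1.1 lists a hemoglobin increase of at least 1.5 g/dL, then OR, then a reduction of at least 4 RBC transfusions per 8 weeks. A closing line follows both: "in comparison to pre-treatment values and lasting at least 8 weeks". The section also states that "measurements after randomization influenced by preceding transfusions within one week will not contribute to the response criteria".

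SAP 2.7.1.1 gives the first limb as "Hemoglobin increased" by at least 1.5 g/dL, then OR, then a reduction of at least 4 "units of RBC transfusions over 8 weeks, in comparison to 8 weeks' pretreatment values, and lasting at least 8 weeks". The duration appears once, at the end of that transfusion sentence: "pretreatment values, and lasting at least 8 weeks". It sets the hemoglobin comparator separately: "In order to measure hemoglobin increase, the last hemoglobin value measured prior to randomization will be used as the pretreated value", or the mean of two values if each is at least 7 days after any transfusion. It says that HI "will be assessed based on International Working Group (IWG) criteria" and that "All episodes of HI in the patient will be considered". It describes all study patients as transfusion dependent. It does not repeat the exclusion for post-randomization values.

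SAP 2.1 says that analysis follows protocol section 10 as detailed in the SAP. SAP Section 4 declares one change to the protocol's analyses, for neutropenia and thrombocytopenia. The SAP change log for Amendment 1 records that the HI definition was clarified.

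**The concern.** A programmer working from SAP 2.7.1.1 finds no duration or confirmation rule for hemoglobin and no rule for values taken soon after a transfusion. Hematology is scheduled every 4 weeks, and the study runs for 3 years after the last enrolment. A patient on treatment therefore has many chances to exceed the threshold once, through ordinary variation or a recent transfusion. Responses of that kind would occur in both arms, raise both percentages and shrink the difference that the endpoint is meant to show.

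**Working it through.** **Text.** The two definitions side by side:

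| Element | Protocol 10.5.1.1 | SAP 2.7.1.1 |
|---|---|---|
| Position of the 8-week duration | Own line after both limbs | Inside the transfusion sentence |
| Comparator in that clause | Pre-treatment values, general | The 8 weeks before treatment, which fits transfusions only |
| Hemoglobin comparator | Last pre-randomization value, or mean of two | Same, stated separately and without a duration |
| Post-randomization hemoglobin within a week after transfusion | Excluded | Not mentioned |

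The wording changed as well as the layout. An 8-week pre-treatment comparator cannot apply to hemoglobin, which has its own. Taken as a unit, the clause belongs to the transfusion limb.

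**Figures.** The documents give no HI response rate, HI power or hemoglobin SD, so there is no plan figure to reproduce. What follows shows only how far the two readings can diverge.

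*Inputs from the documents:* threshold 1.5 g/dL; 4-weekly visits, so 13 values per year; baseline from one or two values; 210 patients at 2:1, so 140 and 70.

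*Assumed:* no true change; within-patient SD 0.5, 0.75 or 1.0 g/dL; autocorrelation 0 or 0.5 between successive values; all visits attended; no transfusion effect.

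*One visit, one baseline value, no autocorrelation:* P(difference ≥ 1.5) = 1 − Φ(1.5 / (SD√2)).
- SD 0.5: 1.5/0.707 = 2.12, giving 1.7%.
- SD 0.75: 1.5/1.061 = 1.41, giving 7.9%.

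Over 13 visits in the same setting, simulation gives 12.3% and 38.2% with at least one such value.

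*All settings* (60,000 simulated patients each). Sustained means three consecutive 4-weekly values spanning 8 weeks. Ranges run over both autocorrelations and both baseline rules:

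| Follow-up | SD (g/dL) | Any single value | Sustained 8 weeks |
|---|---|---|---|
| 1 year | 0.5 | 7–12% | 0–1% |
| 1 year | 0.75 | 31–38% | 2–8% |
| 1 year | 1.0 | 49–57% | 6–17% |
| 3 years | 0.5 | 16–22% | 0–3% |
| 3 years | 0.75 | 51–56% | 4–17% |
| 3 years | 1.0 | 69–77% | 12–31% |

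*Dilution.* If a fraction f of true non-responders is falsely labelled in each arm, the observed rate is p + (1 − p)f and the difference shrinks by the factor (1 − f). Power = Φ[(Δ − 1.96·SE₀)/SE₁], with SE₀ pooled and SE₁ unpooled. Assumed true rates are 25% (n = 140) and 10% (n = 70):

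| f | Deferasirox | Placebo | Difference (points) | Power |
|---|---|---|---|---|
| 0 | 25.0% | 10.0% | 15.0 | 75% |
| 0.10 | 32.5% | 19.0% | 13.5 | 54% |
| 0.25 | 43.75% | 32.5% | 11.25 | 34% |
| 0.50 | 62.5% | 55.0% | 7.5 | 18% |

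For f = 0, the pooled rate is 0.20, SE₀ = √(0.16 × (1/70 + 1/140)) = 0.0586 and SE₁ = √(0.09/70 + 0.1875/140) = 0.0512. Then (0.15 − 0.1148)/0.0512 = 0.69, and Φ(0.69) = 75%.

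**The case against.** The SAP nowhere states that one hemoglobin value makes a responder. It assesses HI on IWG criteria, speaks of episodes, and says that data are analyzed according to protocol section 10, which requires 8 weeks for both limbs. The absence of an HI entry in Section 4 fits no intended change as well as it fits an undeclared one. The placement of a trailing clause is also weak evidence where list layout may have suffered in text extraction. This stands to the extent that a protocol-consistent reading remains possible, so a reader who infers that the SAP prescribes a single-value response goes beyond the text. It does not remove the problem. The transfusion-specific comparator is wording, not layout. SAP 2.1 defers to the protocol only as detailed in the SAP, and the detail that would be programmed lacks both the duration and the exclusion.

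The magnitude is open to fair challenge. SD, autocorrelation, follow-up and response rates are all assumed. HI is assessed during treatment, which can end early, so 39 visits over 3 years cannot be assumed for everyone. The claim that chance responses would swamp durable ones holds only under the less favorable settings; at SD 0.5 over 1 year the false share is 7–12%.

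The stakes are limited too. Tests are exploratory, SAP 2.7.2 says that no hypothesis is tested for secondary endpoints, and no power was planned for HI.

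**Conclusion.** The point holds as a literal departure from the protocol. SAP 2.7.1.1 gives the hemoglobin limb no duration, omits the post-randomization transfusion exclusion, and Section 4 declares neither. Whether the departure was intended cannot be told from the documents.

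If the SAP is followed as written, false hemoglobin responders over 1 year would be about 7–12% instead of 0–1% at SD 0.5 g/dL, and 31–38% instead of 2–8% at SD 0.75. These figures rest on the assumed SD, the autocorrelation and full visit attendance. They contain no transfusion effect, so they do not size the second omission. The loss of power shown also assumes equal false-response rates in both arms and is illustrative, since no planned decision depends on it. What is at risk is the interpretability of the HI percentages and their confidence interval. The primary analysis is unaffected. The SAP should be corrected, but the trial's main conclusion does not depend on it.

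**What to change.** In SAP 2.7.1.1:

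1. Place the clause "in comparison to pre-treatment values and lasting at least 8 weeks" on its own line after both limbs, as in the protocol. Keep the 8-week transfusion comparator as a separate sentence.
2. Restore the exclusion of post-randomization hemoglobin values within one week after a transfusion.
3. Define the hemoglobin limb for programming: an increase of at least 1.5 g/dL sustained across the transfusion-unaffected assessments spanning at least 8 weeks, with a stated rule for missing or excluded visits. The protocol gives the duration but no visit-level rule, so this is an operational choice to fix before unblinding.
4. If a change to the protocol's definition was intended, declare and justify it in Section 4.

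The cost is SAP wording and derivation code. No new data are needed. Fewer patients will count as responders, as the protocol's definition implies.
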